5.2.22. Assessment of Archival Tissue Oncology Biomarkers (Phase IIa only)

An archival tissue sample (either from the diagnostic tumour or a metastatic site) in the form of formalin fixed paraffin embedded (FFPE) tumour block will be collected from each patient. If it is not possible to obtain the entire tumour block, 10-20 slides of unstained 5 micron sections may be provided instead.

Provision of a tumour sample is mandatory. If an archival sample is not available, a fresh tumour biopsy sample must be taken. Tumour samples will be tested for oncology biomarkers.

Further details on sample processing, handling and shipment are provided in the Laboratory Manual.

The following details will be collected: whether archival or fresh tumour, sample tissue type (primary or metastatic), whether representative tumour tissue is present, biopsy site, biopsy type, and histology sample ID.

Archival tumour blocks will be returned to source at the end of the study or earlier, upon request, if required.

5.3. Pharmacokinetics (Safety run-in only)

5.3.1. Collection of Pharmacokinetic Samples

Venous blood samples (2 x 2.7 mL) for determination of concentrations of AZD4547, anastrozole and letrozole in plasma will be taken at the times presented in Table 3 on both day 7 of the NSAID monotherapy and day 7 of cycle 1 of the AZD4547 + anastrozole or letrozole combination therapy. These plasma samples will also be analysed for phosphate and the data used with the AZD4547 PK data to investigate any PK / PD relationship. The date and time of collection of each sample will be recorded.

Table 3: Pharmacokinetic Sampling Schedule for Safety run-in

NSAI¹ monotherapy day 7 and cycle 1 day 7 (AZD4547 + NSAI¹)	
Time relative to dose (hours)	Time window
Pre-dose	N/a
0.5	±10min
1	±10min
2	±15min
3	±15min
4	±15min
5	±15min
6	±30min
8	±30min

¹ Either anastrozole or letrozole

The timing of the PK samples may be adjusted during the study, dependent on emerging data, in order to ensure appropriate characterisation of the plasma concentration-time profiles. The total number of samples and the total volume of blood taken from each patient will not exceed that presented in Table 4. Samples will be collected, labelled, stored and shipped as detailed in the Laboratory Manual.

5.3.2. Determination of drug concentration in PK samples

Samples for determination of AZD4547 concentrations in plasma will be analysed at PRA International, The Netherlands. Samples for determination of anastrozole and letrozole concentrations in plasma will be analysed at Covance, UK, using appropriate bioanalytical methods.

5.3.3. PK Parameter Derivation

The actual sampling times will be used in the parameter calculations and PK parameters will be derived using standard non-compartmental methods.

Where possible the following PK parameters will be reported:

Anastrozole

Last day of NSAI monotherapy: $C_{ss,max}$, $t_{max,ss}$, $C_{ss,min}$, $AUC_{(0-8)}$, $AUC_{(0-t)}$, t , AUC_{ss} , CL_{ss}/F , V_{ss}/F , metabolite:parent ratio

Cycle 1 Day 7: $C_{ss,max}$, $t_{max,ss}$, $C_{ss,min}$, $AUC_{(0-8)}$, $AUC_{(0-t)}$, t , AUC_{ss} , CL_{ss}/F , V_{ss}/F , metabolite:parent ratio, ratio of C_{max} Cycle 1 Day 7 / C_{max} last day of NSAI monotherapy, ratio of AUC_{ss} Cycle 1 Day 15 / AUC_{ss} Last day of NSAI monotherapy

Letrozole

Last day of NSAI monotherapy: $C_{ss,max}$, $t_{max,ss}$, $C_{ss,min}$, $AUC_{(0-8)}$, $AUC_{(0-t)}$, t , AUC_{ss} , CL_{ss}/F , V_{ss}/F , metabolite:parent ratio

Cycle 1 Day 7: $C_{ss,max}$, $t_{max,ss}$, $C_{ss,min}$, $AUC_{(0-8)}$, $AUC_{(0-t)}$, t , AUC_{ss} , CL_{ss}/F , V_{ss}/F , metabolite:parent ratio, ratio of C_{max} Cycle 1 Day 15 / C_{max} Last day of NSA1 monotherapy, ratio of AUC_{ss} Cycle 1 Day 15 / AUC_{ss} Last day of NSA1 monotherapy

AZD4547

Cycle 1 Day 7: $C_{ss,max}$, $t_{max,ss}$, $C_{ss,min}$, $AUC_{(0-8)}$, $AUC_{(0-12)}$, $AUC_{(0-t)}$, t , AUC_{ss} , CL_{ss}/F , V_{ss}/F

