1.5. Aromatase Inhibitors

1.5.1. Pharmacokinetic Considerations of the Combination Therapy

The pharmacokinetics and metabolism of letrozole and anastrozole are well understood¹⁰. A key question for us is whether we anticipate any interactions with AZD4547. Letrozole with continuous oral dosing reaches a steady state at 2-6 weeks. The drug is cleared through hepatic metabolism via CYP3A4 and CYP2A6 and subsequent urine clearance. Anastrozole reaches a steady state after 7 days and is 40% plasma protein bound. It is also metabolised in the liver and cleared via the kidneys. It has no effect on CYP2A6 but can inhibit CYP1A2 and CYP2C8 albeit at higher concentrations (2 logs) than clinically used. AZD4547 binding to human serum albumin and to human α 1-acid glycoprotein was 93.2% and 69.6% respectively. One of the principal metabolites formed by human hepatocytes was found in the rat, but other human metabolites were not formed in significant amounts in any non-clinical species. CYP3A4, CYP3A5 and CYP2D6 are likely to be responsible for the metabolism of AZD4547 in vivo, although CYP1A1 turnover may be important in smokers. AZD4547 produced competitive inhibition of CYP3A4/5 using testosterone as the probe substrate, but not with midazolam, and it was also shown to be a time dependent inhibitor of the same isozymes.

From the above, we do not anticipate any problems with the combination of anastrozole and AZD4547. However, there is a small possibility that letrozole and AZD4547 may interact through one of their common metabolising enzymes CYP3A4. Nevertheless, AstraZeneca have in house data showing that other drugs using this pathway are unaffected by AZD4547 suggesting that this issue may not be clinically relevant. On this basis, the safety run-in part of the trial has been designed to start using the pharmacologically active, tolerated, dose defined from the currently running Phase I AZD4547 trial with the usual clinical dosing used for either anastrozole or letrozole.

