3.2. Treatment Regimens

Safety run-in:

Initially, patients will continue to receive the single agent treatment which they have progressed on: either anastrozole (1mg) or letrozole (2.5mg), orally, once daily for 7 days. N.B. this must be preceded by a minimum of 21 days of anastrozole or letrozole treatment prior to study entry.

Oral AZD4547 will then be added to this ongoing non-steroidal aromatase inhibitor therapy twice daily but on an intermittent schedule of one week on/one week off.

Phase IIa:

[figure not shown]
Patients will continue or restart the NSAI which they have progressed* on: either anastrozole (1mg) or letrozole (2.5mg), orally, once daily but together with twice daily AZD4547 (80mg); the confirmed dose level for AZD4547 determined during the safety run-in part of the study.

*Prior to study entry, patients must have taken anastrozole or letrozole at some stage in their treatment to date for breast cancer; and shown evidence of resistance to this therapy. The NSAI does not have to be the most recent line of treatment.

AZD4547 will be given on an intermittent schedule of one week on / one week off. This schedule has been well tolerated in the preceding safety run-in part of the study. However, if 2 or more cases of severe toxicity (leading to permanent discontinuation of study drug) are observed in the first 6 patients, the Independent Data Monitoring Committee (IDMC) will consider an alternative schedule of two weeks on / one week off, if emerging data from other AZD4547 studies suggest that this is a better tolerated schedule.

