6.2.3. Dosage and Duration

AZD4547 will be administered orally twice daily in a tablet formulation. A cycle of treatment will be defined as 28 days: one week of AZD4547 twice daily in combination with either anastrozole or letrozole once daily, followed by one week of either anastrozole or letrozole once daily alone, and the intermittent schedule repeated once more to complete one cycle.

For procedures relating to dose modification, dosing interruption and restarting of AZD4547 for subjects in both the safety run-in and phase IIa study, see 6.2.8.

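### Section 5.3.3 defines three of the four aromatase-inhibitor interaction ratios on Cycle 1 Day 15, a day with no PK samples, so they cannot be computed as written

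*Protocol*

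**What the plan says.** Section 2.2 makes the comparison of anastrozole or letrozole PK alone and in combination the first secondary objective of the run-in. Section 5.3.1 says when blood is drawn: "day 7 of the NSAID monotherapy and day 7 of cycle 1 of the AZD4547 + anastrozole or letrozole combination therapy". Table 3 gives nine times per day, from pre-dose to 8 hours. The times may be adjusted, but with a cap: "The total number of samples and the total volume of blood taken from each patient will not exceed that presented in Table 4".

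Under its Cycle 1 Day 7 entries, section 5.3.3 lists two ratios to the last monotherapy day for each drug. The anastrozole Cmax ratio uses Cycle 1 Day 7. The anastrozole AUCss ratio is "Cycle 1 Day 15 / AUC_{ss} Last day of NSAI monotherapy", and both letrozole ratios also use Cycle 1 Day 15.

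Section 6.2.3 sets the schedule: a week of AZD4547 with the aromatase inhibitor, "followed by one week of either anastrozole or letrozole once daily alone", and then the same again to fill 28 days.

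On letrozole, section 1.5.1 states: "Letrozole with continuous oral dosing reaches a steady state at 2-6 weeks". Section 3.2 sets the run-in's lead-in before the 7 days of monotherapy: "this must be preceded by a minimum of 21 days of anastrozole or letrozole treatment prior to study entry".

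**The concern.** A ratio defined on a day without samples has no data. Three of the four interaction ratios are in that position, including both for letrozole, the drug for which section 1.5.1 itself raises a possible CYP3A4 interaction with AZD4547. Because section 5.3.3 reports parameters only where possible, the three ratios could simply drop out of the report.

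Sampling on Day 15 would not help. It is the first day back on AZD4547 after days 8 to 14 without it, so it would not show the aromatase inhibitor under steady co-administration.

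Two lesser points bear on the same comparison. Both inhibitors are given once daily, so AUCss covers 24 hours while sampling stops at 8. And the minimum lead-in does not guarantee letrozole steady state on the reference day at the slow end of the protocol's own range. Any remaining accumulation would raise the ratio in the same direction as CYP3A4 inhibition.

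**Working it through.** **1. Is there room for a Day 15 profile?**
- Inputs: 9 time points per PK day (Table 3); 2 PK days (section 5.3.1; Table 1 marks two days in its PK row); 5.4 mL per sample (2 x 2.7 mL, section 5.3.1); 18 samples and 97.2 mL (Table 4).
- Plan's figure reproduced: 9 x 2 = 18 samples; 18 x 5.4 = 97.2 mL. The Table 4 column also adds up: 30 + 45 + 97.2 + 75 + 5 = 252.2 mL.
- A third profile would need 9 x 3 = 27 samples and 27 x 5.4 = 145.8 mL, above the cap. Freedom to move sample times does not supply a Day 15 profile in addition to the two planned.

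**2. What is Day 15 in the schedule?**
One week on, one week off gives AZD4547 on days 1-7 and 15-21, and none on days 8-14 and 22-28. Day 7 ends the first on-week. Day 15 is a dosing day, but the first after seven days off.

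**3. The four ratios against the sampling days**

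| Ratio to last monotherapy day | Numerator day in 5.3.3 | Sampled? |
|---|---|---|
| Anastrozole Cmax | Cycle 1 Day 7 | yes |
| Anastrozole AUCss | Cycle 1 Day 15 | no |
| Letrozole Cmax | Cycle 1 Day 15 | no |
| Letrozole AUCss | Cycle 1 Day 15 | no |

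Section 5.3.3 also lists Css,max, AUC(0-8) and AUCss for both drugs on both sampled days. Each ratio can be formed once the label reads Day 7.

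**4. Coverage of the dosing interval**
24 - 8 = 16 hours, or two thirds of a once-daily interval, is not sampled after the dose. AUC(0-8) lies wholly within the sampled window on both days.

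**5. Letrozole accumulation at the entry minimum**
- Days on letrozole: 21 + 7 = 28 at monotherapy day 7; 28 + 7 = 35 at Cycle 1 Day 7. The protocol's 2-6 weeks is 14-42 days.
- Assumption (not in the protocol): first-order accumulation, with a share p of steady state reached at T days. Then k = -ln(1 - p)/T, and the ratio with no interaction is (1 - exp(-35k)) / (1 - exp(-28k)).

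| T | p | Ratio with no interaction |
|---|---|---|
| 42 days | 0.90 | 1.088 |
| 42 days | 0.95 | 1.062 |
| 42 days | 0.99 | 1.026 |
| 28 days | 0.90 | 1.049 |
| 28 days | 0.97 | 1.018 |
| 14 days | 0.90 | 1.007 |
| 14 days | 0.97 | 1.001 |

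The excess shrinks with longer prior treatment. In the least favourable row (T = 42, p = 0.90, k = 0.0548), a patient with 42 days at the reference visit has (1 - exp(-49k)) / (1 - exp(-42k)) = 0.932/0.900 = 1.035.

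**The case against.** The best defence is that this is a labelling slip. The three ratios stand among the Cycle 1 Day 7 entries, the parallel anastrozole Cmax ratio says Day 7, and every passage on PK timing says Day 7. An analyst with no Day 15 data would find the right values in the same list. That is probably how the error arose. It makes the correction easy but does not remove the need for it.

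A reader might infer that the PK objective cannot be answered. The protocol does not support that: sections 2.2 and 2.4 name no day and no ratio, and the component parameters are listed for both sampled days.

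A reader might also take section 8.2.4, which keeps the PK derivation rules out of the SAP, to mean that 5.3.3 is the only definition of these ratios. That section deals with missing, unused and spurious concentration data and refers to rules held by the PK scientist. It does not bear that weight.

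On AUCss, the pre-dose sample can stand in for the 24-hour value, and AUC(0-8) is already listed. This is fair, but the substitution itself assumes steady state, so a ratio on the observed window is still worth adding.

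On letrozole, run-in patients must have relapsed or progressed during aromatase-inhibitor treatment, so 21 days is a floor that few are likely to sit near. With 3 to 12 patients in the letrozole run-in, limiting the comparison to those with longer exposure could leave very few. Both objections stand, and the point supports a sensitivity display only.

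**Conclusion.** Section 5.3.3 contradicts section 5.3.1 and Tables 1, 3 and 4. Three of the four interaction ratios, including both for letrozole, name a day on which none of the 18 planned PK samples falls, and they cannot be computed as written. This rests on the protocol's text and arithmetic alone. The objective remains answerable from the parameters listed for the two sampled days.

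The letrozole point is minor and conditional. A no-interaction ratio could be inflated by about 3-9% at the 21-day minimum if 90-99% of steady state is reached only at 6 weeks. It would be inflated by under 1% if at least 90% is reached at 2 weeks. The shares of steady state are assumptions; the 2-6 weeks is the protocol's.

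Neither the DLT assessment nor the phase IIa primary analysis depends on these ratios.

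**What to change.** In section 5.3.3:

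1. Replace Cycle 1 Day 15 with Cycle 1 Day 7 in the anastrozole AUCss, letrozole Cmax and letrozole AUCss ratios.
2. Add, for each drug, the ratio of AUC(0-8) on Cycle 1 Day 7 to AUC(0-8) on the last monotherapy day, beside the AUCss ratio.
3. As a sensitivity display only, list separately the letrozole patients with less than 6 weeks of treatment at monotherapy day 7. Take start dates from the concomitant-medication record (section 5.2.10), which Table 1 schedules at run-in screening. Table 1 has no endocrine-therapy row, so the section 5.2.5 data cannot be relied on for these patients.

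The first two changes are wording and one added ratio; the planned 18 samples and 97.2 mL suffice. The third needs each patient's letrozole start date to be in the concomitant-medication data. It removes no patient from the main comparison.

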5.4. Pharmacodynamics

5.4.1. Safety Run-In

Blood samples (3 x 5ml) will be collected to provide two samples of plasma and one sample of serum per time point, as indicated in Table 1. These will be analysed for a range of oncology biomarkers including FGF23 and FGF2, which may correlate with drug response. The date of collection and sample IDs will be recorded on the eCRF.

5.4.2. PIIa

Blood samples (2 x 5ml) will be collected to provide one sample of plasma and one sample of serum per time point, as indicated in Table 2. These will be analysed for a range of oncology biomarkers, which may correlate with drug response. The date of collection and sample IDs will be recorded on the eCRF.

5.5. Exploratory Research

5.5.1. Biomarker research

Where a patient agrees to take part in the exploratory research aspect of the study, biological samples e.g. archived and study-specific tumour samples will be collected and may be analysed for biomarkers to investigate possible relationships with disease status, efficacy of study drug and outcome. These results may be reported separately from the clinical study report (CSR).

5.5.1.1. Collection of Archival Tumour Tissue Samples (Safety run-in)

This part of the study is optional. Where patients consent to take part, an archival tissue sample (either from the diagnostic tumour or a metastatic site) in the form of formalin fixed paraffin embedded (FFPE) tumour block will be collected. If it is not possible to obtain the entire tumour block, 10-20 slides of unstained 5 micron sections may be provided instead.

The following details will be collected: tissue obtained (yes / no), sample tissue type (primary or metastatic), whether representative tumour tissue is present, biopsy site, biopsy type, histology sample ID, whether FGFR FISH assessment was undertaken, date of assessment, FGFR1 FISH score.

5.5.1.2. Exploratory Research on Archival Tumour Tissue Samples (Phase IIa)

This part of the study is optional. Where patients consent to take part, 5-10 slides of unstained 5 micron sections will be taken from the archival tumour sample for exploratory research.

If archival tumour tissue was not available for mandatory assessment of oncology biomarkers, and a fresh tumour biopsy was obtained for this purpose (see 5.2.22), then slides from this new FFPE block may be used instead.

Further details on sample processing, handling and shipment are provided in the Study Manual.

Archival tumour blocks will be returned to source at the end of the study or, upon request, earlier if required. These samples are classified as research samples and will be registered with the Imperial College Healthcare NHS Tissue Bank (ICHTB).

The following details will be collected: whether slides taken; date slides taken and histology sample ID.

5.5.1.3. Collection of Paired Tumour Biopsies

This part of the study is optional. Where patients consent to take part, tumour biopsies should be collected prior to initiation of treatment (i.e. once the patient has been confirmed to be eligible by the RADICAL study team) and on cycle 1 day 22 (within 18 hours of administration of previous AZD4547 dose). It is strongly encouraged that at least the first biopsy is taken.

The following details will be collected: date of biopsy collection, biopsy site, biopsy type and histology sample ID.

5.5.2. Circulating Tumour Specific DNA (Phase IIa only)

Where a patient agrees to take part in the optional ctDNA study, 10 ml of blood will be collected at each of the time-points indicated in Table 2 to provide a plasma sample for ctDNA analysis. The date of collection and sample ID will be recorded on the eCRF.

The results of this research will not form part of the CSR.

5.5.3. Pharmacogenetics

Where the patient agrees to take part in the optional pharmacogenetics study, a single blood sample (1 x 5ml) will be collected to provide a plasma sample for genetic analysis. This should be obtained immediately prior to starting study treatment. The date of collection and sample ID will be recorded on the eCRF.

The results of this research will not form part of the CSR.

5.6. Chain of Custody of Biological Samples

In all cases, patients will be consented for the collection and use of their biological samples and a full chain of custody will be maintained for all samples throughout their lifecycle.

The investigator at each site is responsible for maintaining a record of full traceability of biological samples collected from patients while these are in storage at the site, either until shipment or disposal.

Any person(s) responsible for temporarily holding samples, e.g. sub-contracted service provider keeps full traceability of samples from initial receipt of sample to further shipment or disposal (as appropriate).

Imperial College keeps overall oversight of the entire lifecycle through internal procedures and monitoring of study sites

Samples retained for further use will be registered with the Imperial College Healthcare NHS Tissue Bank (ICHTB).

5.7. Total Blood Volumes

The total volume of blood that will be drawn from each patient in this study is shown in Table 4 for the safety run-in and in Table 5 for phase IIa. The number of samples taken, and the volume required for analysis, may change during the course of the study as new data becomes available.

Table 4: Volume of Blood to be Drawn from each Patient during Safety run-in

	Screening, NSAID ^c monotherapy and Cycle 1			Cycle 2 (and each subsequent cycle ^b)			Treatment discontinuation / 28 day Follow-up		
	Sample volume (mL)	Number of samples	Total volume (mL)	Sample volume (mL)	Number of samples	Total volume (mL)	Sample volume (mL)	Number of samples	Total volume (mL)
Clinical chemistry ^a	6	5	30	6	1	6	6	2	12
Haematology ^a	9	5	45	9	1	9	9	2	18
Pharmaco-kinetics	5.4	18	97.2	-	-	-	-	-	-
PD biomarkers	15	5	75	-	-	-	15	1	15
Pharmaco-genetics	5	1	5	-	-	-	-	-	-
Total			252.2			15			45

^a exact volume of blood for clinical chemistry and haematology may vary depending on local practice

^b total volume in subsequent cycles may vary, but volume in any one cycle will not exceed the volume required at Cycle 2

^c Either anastrozole or letrozole

Table 5: Volume of Blood to be Drawn from each Patient During Phase IIa

	Screening and Cycle 1			Cycle 2			Cycle 3 (and each subsequent cycle ^b)			Treatment discontinuation / 28 day Follow-up		
	Sample volume (mL)	Number of samples	Total volume (mL)	Sample volume (mL)	Number of samples	Total volume (mL)	Sample volume (mL)	Number of samples	Total volume (mL)	Sample volume (mL)	Number of samples	Total volume (mL)
Clinical chemistry ^a	6	5	30	6	2	12	6	1	6	6	2	12
Haematology ^a	9	5	45	9	2	18	9	1	9	9	2	18
PD biomarkers	10	4	40	10	1	10	10	1	10	10	1	10
Pharmaco-genetics	5	1	5	-	-	-	-	-	-	-	-	-
ctDNA analysis	10	5	50	10	2	20	10	1	10	10	2	20
Total			170			60			35			60

^a exact volume of blood for clinical chemistry and haematology may vary depending on local practice

^b total volume in cycle 3 and subsequent cycles may vary, but volume in any one cycle will not exceed the volume required at Cycle 2

6. STUDY TREATMENT

6.1. Non Investigational Medicinal Products

Anastrozole (1mg once daily, orally) and letrozole (2.5mg once daily, orally) will be prescribed according to usual practice and dispensed from either site specific hospital stock or via the General Practitioner. Compliance to these treatments will be recorded using Patient Diary cards and all data transferred to the eCRFs.

6.2. Investigational Medicinal Product

Safety run-in: AZD4547 is manufactured by Pharmaceutical Development R&D, AstraZeneca UK according to Good Manufacturing Practice.

The investigational product is provided as, 20mg white, film-coated tablets containing AZD4547.

Phase IIa: AZD4547 is manufactured by Pharmaceutical Development R&D, AstraZeneca UK and AstraZeneca R&D Mölndal, according to Good Manufacturing Practice.

The investigational product is provided as, 20mg beige; film-coated tablets containing AZD4547.

